Data Analysis: For between-arm comparisons of single valued (either measured at once or as an aggregated variable such as AUC over a period) outcomes, we will apply chi-square test if the outcome is binary, and *t*-test or Mann-Whitney *U*-test to continuous outcomes based on the best fit of Shapiro-Wilk's test. The between-arm difference in the distributions of times to the first event and multiple events (of the six constituents) will be examined by using single event time Cox's model and the times to correlated multiple events using Cox's model allowing multivariate frailty, respectively. The incidence rates of each individual event, with- and without differentiating its severity, as a binary outcome will be compared between the two arms by means of longitudinal logistic modeling with generalized estimating equation (GEE)⁸⁴ to allow more than one events per patient. For the repeated measures analysis of the longitudinal plasma mitochondrial DNA and urine 3- methylhistidine (3-MH), we will examine if the mean levels over time are different between the two arms by using longitudinal general linear mixed effects model⁸⁵ which will provide the within group time dependency patterns as a linear effect or more complex form of non-linear patterns which would be able to characterize the time dependent treatment effects over time along with testing for time \times group interaction(s) of those model parameter(s). Total and organ-specific SOFA scores over time will also be examined by this mixed effects models of which the

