particular interest is to test if the improvement in the longitudinal mean SOFA scores is greater during certain time window. All analyses will also be extended to adjust for the influencing effects of any baseline demographic and/or clinical indications. Missing data may be unavoidable. Because the informed consent from many study enrollees will be obtained through the family members (i.e., surrogates), a small portion (up to 2% attrition rate) of the enrolled patients may voluntarily withdraw from the study. Before final analysis, we will check the missing data pattern of the outcomes first. If there are systematic differences in missing data patterns between the study groups and/or patient characteristics (e.g., burn type), we will take into account such problems in the analysis. The longitudinal mixed effects modeling will provide unbiased and consistent estimates of the effects provided that the missing data mechanism is ‘missing at random’ (MAR). If necessary, multiple-imputation will be applied to all endpoints analyses. All statistical tests will be two-sided and will adopt a 5% significance level.

Sample size calculation: The sample size of 290 study patients for this study is determined to achieve an adequate statistical power at a 5% Type-1 error rate for the primary endpoint analysis by the following statistical calculations. We first estimated the expected means and variances of the composite scores (assuming the six individual events are independent) for the Control and CoQ10 treatment arms under the assumption depicted in **Table 6** via 1000 repeated simulated data sets ($n = 5000$ each), instead of calculating them algebraically.

Each simulation run calculated the means and variances of the two arms, and the resulting average means (and variances) over 1000 simulations were 2.43 (1.04) in the placebo arm and 1.94 (1.05) in CoQ10 arm respectively. Based on the assumption about the event incidence rates and the estimated means and variances of the composite scores from the simulated data sets, the calculated required sample size per treatment arm (using PASS¹¹⁰) to detect such a difference (i.e., 20% reduction in the overall events) with 80% power at a 5% Type-1 error rate using 2-sided independent samples t-test was 142 per arm.

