We have estimated the incidence rates of dysfunction of each organ or system and mortality under the null hypothesis (H_0), which are listed below in **Table 6** (Control Arm), based on previous studies^{6,46,48,59,60,64,74,86-95} and [name] pilot study.

Table 6. Elements of the composite endpoint and their assumed incidence rates	Control Incidence Rate	CoQ10 Incidence Rate
Acute Kidney Injury (KDIGO) (Stage 1 -3)	40%	32%
ARDS (Berlin Definition) (Mild – Severe)	40%	32%
Cardiovascular Dysfunction (Score 1 - 4)	70%	56%
Coagulopathy (Score 1 - 4)	70%	56%
Liver dysfunction (Score 1 - 4)	10%	8%
Death (All Causes)	8%	6.4%

Quarterly Enrollment Target: 290 burn patients will be enrolled at the 15 sites and each site is anticipated to enroll 19 patients during the study period. The quarterly enrollment targets are shown below in **Table 7**.

Table 7	Year 1				Year 2				Year 3				Year 4			
	Q1	Q2	Q3	Q4												

Quarterly	-	-	24	24	25	24	24	25	24	24	25	24	24	25	-	-
Cumulative	-	-	24	48	73	97	121	146	170	194	219	241	265	290	290	290

DATA MANAGEMENT AND DATE SAFETY MONITORING PLAN

Data management: Data will be housed in a secure database at the University of California Davis Data Coordinating Center (UCD-DCC). The UCD-DCC will utilize the RedCap data management tool to manage this clinical study. Records containing PHI will be managed according to the requirements of the HIPAA Privacy Rule. All subject case study forms and records will be de-identified and assigned a unique study number to protect patient privacy and maintain confidentiality. PHI will be maintained at the participating sites for the purpose of data verification. Any hard copy source documents will be stored in a locked file at each site for a minimum of three years after study closure and completion of analysis. If any information from this study is presented at scientific meetings or published, subject names and PHI will not be used.

Data safety monitoring plan and interim analysis: We will follow the guidelines of the DoD to form the Data Safety Monitoring Board (DSMB). The DSMB will monitor the overall status of the trial: number of patients enrolled overall and per each center, adherence to protocol overall and per center and results of the interim analysis.

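### The stated requirement of 142 patients per arm does not follow from the plan's own inputs, which need 70 per arm (stated means and variances) or 75 per arm (Table 6)

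*Combined protocol and SAP*

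**What the plan says.** The Sample size calculation section opens: "The sample size of 290 study patients for this study is determined to achieve an adequate statistical power". It describes a simulation of the 0–6 composite score (1000 data sets of 5000) from the rates in Table 6, "assuming the six individual events are independent". The resulting average means, with variances in brackets, "were 2.43 (1.04) in the placebo arm and 1.94 (1.05) in CoQ10 arm respectively". The target is a 20% reduction in overall events. The number needed "with 80% power at a 5% Type-1 error rate using 2-sided independent samples t-test was 142 per arm".

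Table 6 ("Elements of the composite endpoint and their assumed incidence rates") gives these control and CoQ10 rates:

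- AKI and ARDS: 40% and 32% each
- cardiovascular dysfunction and coagulopathy: 70% and 56% each
- liver dysfunction: 10% and 8%
- death: 8% and 6.4%

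The Data Analysis section expects that "a small portion (up to 2% attrition rate) of the enrolled patients may voluntarily withdraw from the study". The sample size paragraph does not refer to this figure. It also mentions no correlation between events, no variance inflation and no allowance for the Mann-Whitney fallback.

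**The concern.** The paragraph prints everything a two-sample t-test calculation needs, so the result can be checked directly. A difference of 0.49 with a variance near 1.05 is a standardised effect of about 0.48, and 142 per arm looks about twice too large for that. The simulated means are also higher than the sums of the Table 6 rates, so there may be two separate breaks: from Table 6 to the moments, and from the moments to the number of patients.

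This paragraph is the only justification in the documents for enrolling 290 patients. If 142 is really a total over both arms, the apparent margin is accidental. If it rests on a larger variance that is not reported, the independence statement does not describe the calculation that was done. The two cases mean different things for the trial's real power, and the text does not let a reader tell them apart.

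**Working it through.** **Inputs.** Two-sided 5% level, 80% power, independent samples t-test, means and variances: Sample size calculation. Equal arms: opening of the statistical section (balanced two-arm design). Event rates: Table 6. All results in steps 1 to 4 assume independent events.

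**1. Attempt to reproduce 142 from the stated moments.** The normal approximation is

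n per arm = (z₀.₉₇₅ + z₀.₈₀)² × (V₁ + V₂) / Δ²

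= (1.960 + 0.842)² × (1.04 + 1.05) / (2.43 − 1.94)²

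= 7.849 × 2.09 / 0.2401 = 68.3, so 69.

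The exact noncentral t calculation gives 69.3, so **70 per arm** (power 0.798 at 69 and 0.804 at 70). The figure of 142 is not reproduced. Power at 142 per arm is about 98%.

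**2. The moments implied by Table 6.** Under independence the mean is Σp and the variance is Σp(1 − p).

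- Control mean: 0.40 + 0.40 + 0.70 + 0.70 + 0.10 + 0.08 = 2.38
- CoQ10 mean: 0.32 + 0.32 + 0.56 + 0.56 + 0.08 + 0.064 = 1.904
- Control variance: 0.24 + 0.24 + 0.21 + 0.21 + 0.09 + 0.0736 = 1.0636
- CoQ10 variance: 0.2176 + 0.2176 + 0.2464 + 0.2464 + 0.0736 + 0.0599 = 1.0615

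The standard error of a mean over 1000 × 5000 draws is √(1.0636 / 5,000,000) ≈ 0.0005. The gap in the control mean, 2.43 − 2.38 = 0.05, is about 100 times that. A full re-run of the described simulation gave means 2.379 and 1.905 and variances 1.063 and 1.062.

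With Δ = 0.476, the normal approximation is 7.849 × 2.1251 / 0.2266 = 73.6, and the noncentral t gives 74.6, so **75 per arm** (power 0.797 at 74 and 0.802 at 75). Power at 142 per arm is 97.2%. Simulated t-test power (20,000 trials) was 0.802 at 75 and 0.970 at 142.

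**3. Readings that might rescue 142.**

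| Reading | Needed per arm |
|---|---|
| Stated moments | 70 |
| Stated moments, over the rounding of the printed figures | 67 to 73 |
| Bracketed values taken as SDs | 73 (69 to 77 over rounding) |
| Table 6 | 75 |
| Table 6, Mann-Whitney by simulation | about 78 (power 0.807) |

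None comes near 142. For 142 per arm to be needed at 80% power, the variance would have to be about 2.16 (difference 0.49) or 2.04 (difference 0.476). That is about double what is stated, and it does not fit independent events.

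**4. What 142 per arm can detect with 80% power.** With the stated moments, a difference of 0.341, which is 0.341 / 2.43 = 14.0%. With all Table 6 rates scaled together, a reduction of about 14.5% (power 0.801; a 14.0% reduction has 0.772).

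**5. Possible origins, neither established.**

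- If one 70%/56% row had been 75%/60% when the simulation was run, the means would be 2.43 and 1.944 and the variances 1.041 and 1.055, very close to the printed moments. The requirement would then be 70.6, so 71 per arm, and 2 × 71 = 142 in total.
- The step to 290 fits the 2% attrition: 142 / 0.98 = 144.9, so 145 per arm, and 2 × 145 = 290.

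**6. Sensitivity to correlation.** The documents give no correlation, so this range is an assumption: Table 6 rates, with a common correlation r between latent normal variables behind the six events.

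| r | 0 | 0.1 | 0.2 | 0.3 | 0.4 | 0.5 |
|---|---|---|---|---|---|---|
| Control variance | 1.06 | 1.33 | 1.59 | 1.85 | 2.11 | 2.37 |
| Power at 142 per arm | 97% | 94% | 89% | 84% | 79% | 74% |

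**The case against.** The best defence is that nothing in the conduct of the trial changes. The error is conservative, 290 stands, and endpoint, analysis and Type I error are untouched, so this is a fault of documentation. That is fair, and it limits the severity. It does not make the paragraph correct.

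The step from 142 to 290 can be worked out from the 2% attrition given just before the sample size paragraph. That also stands in large part; one confirming sentence from the sponsor is enough.

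The 75%/60% reconstruction needs a rate the plan does not print, and its CoQ10 variance of 1.0551 would round to 1.06, not 1.05. The excess over the rounding boundary is only 0.0001, within simulation error, so the fit survives. The printed moments themselves give a total of 140, not 142, and an unreported larger variance is another possible cause. The reconstruction is therefore only something to check.

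The mismatch with Table 6 moves the requirement only from 70 to 75 and does not explain 142. True; it is a second fault, not the cause of the first.

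Finally, the plan's reference to "times to correlated multiple events" concerns the frailty model for event times, not the primary score, and independence is an openly stated simplification. That is correct, so the correlation table is optional. But a power of 97% should not be written into the plan without its independence condition.

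**Conclusion.** The concern holds. From the plan's own inputs, under its stated independence assumption, 80% power with a two-sided 5% t-test needs 70 per arm (stated moments) or 75 per arm (Table 6), not 142. The stated moments do not follow from Table 6 either, by a margin that simulation error cannot explain. At 142 per arm the power for a 20% reduction is about 98% (stated moments) or 97% (Table 6), and 80% power is reached for reductions of about 14.0% or 14.5%.

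These figures check the paragraph; they do not forecast the trial's power. In the assumed range above, power falls below 80% at a latent correlation of about 0.4. The documents do not show which part is out of date or how 142 arose. This should be fixed, but it does not threaten the validity of the trial.

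**What to change.** Keep 290 patients and make these changes to the Sample size calculation section:

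1. Reconcile Table 6 with the stated means and variances; either may be out of date. Check in the software output whether 142 is the number per arm or the total, and which variance was entered.
2. Restate the power from the reconciled inputs. If Table 6 is right: *Assuming independent events and the Table 6 rates, 142 patients per arm with outcome data give about 97% power for a 20% reduction and 80% power for a reduction of about 14.5%.* If the stated moments are right, the figures are about 98% and about 14%.
3. State how 142 per arm becomes 290. Dividing by 0.98 gives 145 per arm, but the sponsor should confirm that this was the step.
4. Optionally, add a table of power by assumed correlation between events, labelled as an assumption.

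The cost is one recalculation and a revised paragraph, with no change to enrolment, endpoint or analysis. The optional table may show power below 80% at the higher assumed correlations.

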3-Methylhistidine concentrations will be quantified by negative chemical ionization gas chromatography mass spectrometry as described in our previous studies^{52,53}. Urinary creatinine concentrations will be measured by a commercial kit. The average of three measurements on the three consecutive days at each time point will be used for statistical analysis to minimize possible day-to-day variations.

STATISTICAL ENDPOINTS AND APPROACH TO DATA ANALYSIS

This two-arm balanced double blind parallel Randomized Clinical Trial (RCT) study will be performed using an intention to treat (ITT) analysis population that includes all randomized patients.

Primary endpoint: The primary endpoint will be the count of the following events. This count will be used to create a composite score ranging from 0 to 6 by assigning 1 to each event regardless of stage, scores and severity that individual subjects encounter from 72 hours after burn injury through 12 weeks or until death or discharge, whichever occurs first:

1. Acute Kidney Injury (AKI) (KDIGO Stages 1 – 3)
2. ARDS (The Berlin ARDS Definition: Mild, Moderate, Severe)
3. Cardiovascular Dysfunction (SOFA Scores 1 – 4)
4. Coagulopathy (SOFA Scores 1 – 4)
5. Liver dysfunction (SOFA Scores 1 – 4)
6. Death (all causes)

We will calculate mean values of the composite sum scores among the study patients in the CoQ10 and placebo arms, and then test their difference by using an independent samples *t*-test if the observed data are evident to follow a normal distribution by Shapiro-Wilk's test. Otherwise, Mann-Whitney U test will be applied and the group specific medians and quartiles will be used as the summary statistics.

AKI: AKI represents the acute loss of kidney function and is associated with a profound and severe increase in morbidity and mortality in burn patients⁵⁴. Early AKI, which occurs less than 3 days post-burn, is usually related to inadequate fluid replacement during the initial resuscitation. AKI can occur later in the hospitalization and late AKI is multifactorial in origin and often associated with sepsis development⁵⁵. For the purposes of this study, we will follow the definitions and classification guidelines set forth in "AKI of Kidney Disease: Improving Global Outcomes (KDIGO)"^{56,57} (**Table 3**). Published in 2012, this guideline has been used in critically ill patients and in combat-injured populations⁵⁸.

Stage	Table 3. AKI (KDIGO)

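### Does the unspecified interim analysis, alongside a flat 5% significance rule, push the trial's false-positive rate above 5%?

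*Combined protocol and SAP*

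**What the plan says.** The interim analysis appears in one place, the section on data safety monitoring and interim analysis. After enrolment overall and per center, the DSMB's list of things to monitor ends with "adherence to protocol overall and per center and results of the interim analysis". Nothing there or elsewhere says what is analysed, when, how often, or against what boundary.

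The significance rule closes the Data Analysis section: "All statistical tests will be two-sided and will adopt a 5% significance level". The sample size section says the number of patients was chosen "to achieve an adequate statistical power at a 5% Type-1 error rate for the primary endpoint analysis", and that the number required "with 80% power at a 5% Type-1 error rate using 2-sided independent samples t-test was 142 per arm". No part of the 5% is reserved for an earlier look.

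Three other places show what the DSMB is for. Risk management and emergency response has it convene over unforeseen risks and protocol changes. The second project milestone has it share in monitoring human subjects protection, compliance, data quality and enrolment pace. The third milestone puts all statistical analysis of clinical data and biomarkers in the second half of Year 4 and lists no interim analysis.

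**The concern.** An interim analysis is named, and the only significance rule covers all tests without exception. Put together, these can be read as allowing a between-arm comparison of the primary endpoint partway through at 5%, and the same comparison again at the end at 5%. Two chances at 5% do not give a 5% trial.

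On that reading, the trial could stop early or claim success on an interim p just below 0.05. The effect estimate at such a stop would tend to be too large, and the final p-value would be held to a threshold that ignores the earlier look. The Type-1 error rate stated for the primary endpoint would then be wrong.

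**Working it through.** **Inputs from the plan.** Two-sided 5% for all tests (Data Analysis); 5% and 80% power for one t-test (Sample size calculation); 142 per arm, up to 2% attrition and 290 in total (same two sections). **Assumptions, not in the plan:** the number and timing of any interim looks, and that they test efficacy.

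**1. The plan's own figures.** One final test at |Z| > 1.960 has error 0.05, as stated. The total follows from the per-arm figure and attrition alone: 142 / (1 − 0.02) = 144.9, rounded up to 145 per arm, and 2 × 145 = 290. Nothing was added for an interim efficacy look, so the design is that of a single-test trial.

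The 142 itself does not follow from the stated means and variances, "2.43 (1.04) in the placebo arm and 1.94 (1.05) in CoQ10 arm respectively". With the normal formula, n = (1.960 + 0.842)² × (1.04 + 1.05) / 0.49² = 68.3, so 69 per arm. That is a separate matter and does not affect the error-rate question.

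**2. What an unadjusted efficacy look would do.** For looks at information fractions t₁ < … < t_K = 1, the statistics are jointly normal under the null with corr(Z_i, Z_j) = √(t_i/t_j) for i < j. The overall error is 1 − P(|Z_k| < c_k at every look). With c_k = 1.960 throughout:

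| Assumed efficacy looks before the final test | Overall two-sided error |
|---|---|
| none | 5.0% |
| one, at 75% | 7.3% |
| one, at 67% | 7.7% |
| one, at 50% | 8.3% |
| one, at 33% | 8.8% |
| one, at 25% | 9.1% |
| two, equally spaced | 10.7% |
| three, equally spaced | 12.6% |

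**3. What a strict early boundary would do.** With one look at 50% and the final test left at 5%, the overall error is 5.02% if the interim requires p < 0.001, and 5.10% if it requires p < 0.0031.

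**4. What full adjustment would do.** An O'Brien-Fleming boundary with one look at 50% uses c = 1.977 at the end (p < 0.0480) and 1.977 × √2 = 2.797 at the interim (p < 0.0052). A design with exactly 80% power would keep Φ(1.960 + 0.842 − 1.977) = Φ(0.824), about 79.5%, from its final test at that level.

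**5. What a look without an efficacy claim would do.** A safety, conduct or pooled event-rate review adds no rejection region, so the error stays at 5.0%. A futility stop can only remove rejections. For example, with a binding stop at 50% whenever the interim favours placebo, the one-sided probability of a false claim of benefit falls from 2.50% to 2.47%.

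**6. Which row the text supports.** Rows two to eight of the table need an early between-arm test of the primary endpoint and a rule that turns it into a stop for benefit or a claim of success. The plan has neither. The 5% sentence closes a section on end-of-study endpoint comparisons that speaks of the final analysis and does not mention an interim. The DSMB's described functions are risk, conduct and enrolment. The milestones put all statistical analyses in late Year 4. The text supports the first row.

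**The case for a change.** The strongest case for a change is that the interim is planned, not hypothetical: it is in a section title and its results go to the DSMB. The title names it separately from safety monitoring, and adverse events have their own section, so it cannot simply be assumed to mean adverse-event review. The words on 5% cover all tests. A reader cannot confirm from the document that no unblinded efficacy look will occur, and a policy settled after data have been seen could not be verified. One sentence would remove the doubt at no cost in power.

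Much of this stands. The arithmetic is right, the omission is real, and a combined protocol and SAP would read better if it gave the purpose of the interim. The plan mentions no DSMB charter, so I do not rely on one to supply the detail.

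The step from omission to contradiction does not stand. Saying that an interim comparison is to be tested at 5% supplies a comparison, an endpoint and a stopping rule that the plan does not contain. A sentence ruling out an interim efficacy test would leave the final test, its threshold and the number of patients as they are. Writing in an efficacy look with alpha spending would add a feature the plan never states.

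**Conclusion.** The concern holds only in conditional form: an interim efficacy test at 5% that could end the trial in success would take the error to 7.3–9.1% with one look, and to 10.7% or 12.6% with two or three. Those figures rest on assumed timings and on a decision rule that is absent from the plan. Followed as written, the trial has one success decision, the final primary test, and its error is the stated 5%.

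This is a gap in description that a competent team fills in the ordinary way, with a DSMB review that makes no efficacy claim and a final test at 5%. No change to the analysis, the threshold or the sample size follows. The conclusion would differ if the interim were meant to test the primary endpoint between arms with power to stop for benefit, because the final 5% would then no longer be the whole error of the trial.
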